## 1.0 Background and Rationale

We are at a critical time to examine new, innovative strategies to promote healthy pregnancy and optimize maternal and newborn outcomes. Generating successful strategies will require careful examination of existing service delivery models, challenging the current structure of care provision. One aspect of care, recently identified by the World Health Organization, which merits further research, is group antenatal care (GANC).

Antenatal care has the potential to play a pivotal role in ensuring positive pregnancy outcomes for both mothers and their newborns. Since ANC is widely available and attended by the majority of pregnant women in Ghana without the expected impact on birth outcomes, it is vital to examine the way antenatal health messages are delivered. Pregnant women must receive health information that is accurate and easy to understand for them to make informed choices to improve their health and the health of their baby. A critical component of all ANC is teaching women to recognize the major complications that account for the majority of preventable maternal and newborn deaths. Antenatal care provides an opportunity to promote a healthy lifestyle, to integrate positive health behaviors, and to develop a trusting relationship with a provider and the health system. Interactions during ANC provide the opportunity to identify and treat numerous problems, as well as providing a setting to improve women's health literacy. Patients must receive health messages in a manner that allows them to process and evaluate the information and ultimately use it to impact their own health.

The effectiveness of ANC depends on the multidimensional concept of health literacy. Initially considered only as a patient's ability to read and understand written information, it is now more broadly defined as a person's ability to acquire or access information, understand it, and use the information in ways that promote and maintain good health. Despite a burgeoning emphasis on health literacy in high resource countries, there are a dearth of studies examining interventions to improve health literacy in low-resource settings. Even fewer studies have examined maternal health literacy, defined as the "cognitive and social skills which determine the motivation and ability of women to gain access to, understand, and use information in ways that promote and maintain their health and that of their children". New approaches to improve health literacy are sorely needed in countries where women and newborns continue to die from preventable causes.

**Antenatal care has been delivered the same way for decades.** Clinics and hospitals in low-resource countries are notorious for providing ethnocentric care, privileging northern medical values at the expense of traditional and community values. Yet health literacy is affected by the cultural context in which learning takes place, including, but not limited to, belief systems, traditions, understanding, and communication styles. Transmitting health information in a clinical setting often fails to take into account the social and economic circumstances of patients, therefore not achieving the expected impact on health behaviors. This divide has contributed to a lack of progress in reaching the most vulnerable populations. If pregnant women do not receive health messages in a comprehensible way, they cannot effectively maximize the benefits of the health system. Substantially improving women's ability to understand and utilize health information is

of utmost importance if we are to reach the global targets of 70 maternal deaths per 100,000 live births by 2030 and a neonatal mortality rate of 12 per 1000 live births set by WHO/USAID.

### **1.1 Ghanaian Context**

In 2015, the maternal mortality ratio in Ghana was estimated at 319 per 100,000 live births – placing a woman’s lifetime risk of maternal death at 1 in 74, compared to 1 in 3,800 in the United States. In 2014, while 87.3% of women in Ghana surveyed had attended the minimum standard of 4 antenatal care (ANC) visits, 27% gave birth alone or with a non-skilled attendant. Sixty-eight percent of all deaths among children under age 5 in Ghana happen before a child’s first birthday, with 48% of deaths occurring in the first month of life - making the first 28 days in an infant’s life crucial for survival. Only 22.8% of newborns received the recommended postnatal check-up within the first two days of life between 2012-2014 in Ghana. It should be noted that since 2008 there has been only a marginal decline (3%) in neonatal mortality within Ghana. Ghana is now one of 24 priority countries targeted by the United States Agency for International Development (USAID) to improve maternal and child health and end preventable deaths.

### **1.2 Scientific Premise**

Research has shown community-based women’s groups in low-resource settings catalyze action, provide supportive networks, educate and empower, and lead to substantial increases in neonatal survival. Women’s groups at the community level have been found to devise their own culturally appropriate strategies for prevention of newborn problems, home care support, consultation and referral. Women participating in community groups in Guinea showed an increase in maternal health care-seeking behaviors; with women in community groups more than twice as likely to attend four ANC visits, seek care for signs of complications, and given birth in a health facility. A rigorous systematic review and meta-analysis of seven randomised control trials (119,428 births) found women’s groups at the community level were associated with a 37% reduction in maternal mortality, a 23% reduction in neonatal mortality, and a 9% reduction in stillbirths.

While group ANC has been delivered and studied in high-resource settings for over a decade, it has only recently been introduced as an alternative to individual care in sub-Saharan Africa. Two randomized controlled trials of group ANC using a U.S group-based model verses routine care found women assigned to group care had significantly better antenatal knowledge, greater satisfaction with care, and were less likely to have a preterm birth than those in standard care. In addition, the trials showed more favorable birth, neonatal, and reproductive outcomes in the intervention groups. Although the experimental design of the studies from high-resource countries were scientifically rigorous, findings cannot be generalized to low-resource countries with low literacy rates and high rates of maternal and newborn morbidity and mortality. In sub-Saharan Africa, data from two small studies found ANC delivered in groups to be acceptable and feasible to both women and providers in Ghana, Tanzania, and Malawi. In the U.S., Australia, and the Netherlands, group ANC has improved outcomes in birth weight, preterm birth rates, satisfaction with care, and breastfeeding initiation.

## 2.0 Aims and Objectives

**Aim 1:** To quantify differences in BPCR, knowledge of pregnancy and newborn danger signs and recommended action steps.

### Primary Outcomes

- Ability to identify danger signs in pregnancy (e.g. bleeding, severe headache, blurred vision, fever)
- Birth preparedness and complication readiness (e.g. saved money, identified birth facility and emergency transportation to facility, blood donor)
- Ability to identify newborn danger signs (e.g. poor suck, jaundice, difficulty/fast breathing, and convulsions)

### Secondary Outcomes

- Ability to identify postpartum danger signs (e.g. increased bleeding or large clots; weakness/fainting; fever; pain in abdomen or breasts; painful urination)
- Ability to identify the recommended action steps when a problem is identified (e.g. call for help, have a plan for transportation, identify someone to accompany you to facility, identify someone to care for the family, go straight to the facility, supportive care along the way to the facility)
- Self-efficacy operationalized care-seeking history and health information knowledge

**Aim 2:** To assess behavioral differences in care-seeking patterns (e.g. facility birth rates, postnatal and postpartum care)

### Primary Outcomes

- Attendance at 4+ ANC visits
- Facility birth
- Four postnatal/postpartum check-ups for both mother and newborn in the first 6 weeks after birth

### Secondary Outcomes

- Uptake of modern family planning methods at 6 months postpartum
- Infant immunized per EPI scheduled at 1 year
- Completion of IPTp2 malaria prophylaxis during pregnancy

**Aim 3:** To evaluate the clinical outcomes of mothers and their newborns (e.g. decrease in maternal morbidities and perinatal and neonatal mortality)

### Primary Outcomes

- Maternal pregnancy-related morbidities (puerperal sepsis, delayed postpartum hemorrhage)
- Birth outcome (stillbirth, live birth, early neonatal mortality)

### Secondary Outcomes

- At least two tetanus toxoid vaccines during ANC

- Infant protected against neonatal tetanus
- Hemoglobin level upon hospital admission (dichotomized as normal or anemic (<9.5 g/dL))
- Infant birth weight (normal vs. low (<2500g))
- Repeat pregnancy within one year
- Exclusive breastfeeding at 6 months

We hypothesize that pregnant women randomized into group ANC will exhibit increased health literacy through: 1) increased BPCR, including recognition of danger signs and knowledge of how to respond to such signs; 2) higher rates of care-seeking behaviors, including seeking care for problems identified during pregnancy, higher facility delivery rates, and increased attendance at postnatal and postpartum care; and 3) better clinical outcomes for themselves and their newborns than women who received the routine, individual ANC.

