### **3.0 Research Methods and Study Design**

To accomplish our aims we propose a cluster randomized controlled trial (cRCT) in the Eastern District of Ghana. The study is designed in collaboration with the Dodowa Health Research Center under the direction of [name] (Co-PI). Health facilities were selected based the number of deliveries and average gestational age of women in each facility and matched so that each pair of facilities are similar to each other with regard to these matching factors. For each pair of facilities, one will randomly be assigned to group ANC (intervention) and the other to routine, individual ANC (control). The locations of the chosen facilities ensure that participating facilities will be far enough apart to minimize the likelihood of cross-group contamination. The unit of randomization is the health facility stratified by site and gestational age. Cluster randomization will be produced through nbpMatching package from R software. During the study, 1680 participants will be randomized into 120 groups of 12 to 14 women of the same gestational age at the cluster site. This will result in approximately 8-10 groups per site during the study period.

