### 3.3 Data Collection and Measures

All quantitative data will be collected by trained RAs using encrypted and password protected tablets and the REDCap secure web application for data collection database management. Redcap, a secure web application, is geared to support online or offline data capture for research studies. When internet connection is not available, data will be collected off-line and stored on the encrypted tablet. Once a connection is available, these data will be uploaded, managed, and stored on a secure server.

No data will be collected by clinical providers. Data collection will occur at five time points in both intervention and control arms:

1. Time 0: at ENROLLMENT (in person)
  2. Time 1: at THIRD TRIMESTER (in person)
  3. Time 2: POST BIRTH up to 6 weeks after delivery (in person)
  4. Time 3: SIX MONTHS POSTPARTUM (by phone)
  5. Time 4: ONE YEAR POSTPARTUM (by phone)
- 
- 1) T0: The baseline session occurs immediately following the consent process and will be held for approximately 1 hour. Data will be collected by trained RAs using a structured survey; medial information will be self-reported, and thus, are not protected health information (PHI).
  - 2) T1: This session will occur at the third trimester of pregnancy and will last 45 – 60 minutes. Data will be collected by trained RAs using a structured interview and retrieving data from the ANC card. Data collected from the ANC card are PHI and will be protected.
  - 3) T2: This session will occur in the period immediately to 6 week after delivery and will last 45 – 60 minutes. Data will be collected by trained RAs using a structured interview and information from ANC cards on maternal and newborn clinical outcomes using a pre-determined set of indicators.
  - 4) T3: This session will occur 6-months postpartum; data will be collected via phone by a trained RAs using a structured interview. This session will take approximately 20 - 30 minutes.
  - 5) T4: This session will occur 1-year postpartum; data will be collected via phone by a trained RAs using a structured interview. This session will take approximately 20 - 30minutes.

During all visits midwives will record Clinical Health Related Outcomes (Place of birth, hemoglobin levels, newborn birth weight, maternal & newborn morbidities, stillbirth, postpartum visit within 2 days post birth) on the women's ANC card. These data will be collected by the RA during all study visits except baseline.

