### 3.7 Randomization

There are 14 sites in the study. We randomized these 14 sites into the control group and the intervention group. To improve the balance between the two groups and improve the efficiency of estimating intervention effect, we used the facility type, district of site, and ANC registrant numbers in 2018 to conduct matched randomization. The randomization process were carried out using nbpMatching package from R software.

Control Sites				Intervention Sites			
Facility	Facility Type	District	ANC 2018	Facility	Facility Type	District	ANC 2018
Adawso	Health Center	Akuapim North	403	Akuse	Hospital	Lower Manya Krobo	378
Abiriw	Clinic	Akuapim North	322	Adkukrom	Health Center	Akuapim North	299
Tetteh Quarshie	Hospital	Akuapim North	654	Atua	Hospital	Lower Manya Krobo	715
St Martin's	Hospital	Lower Manya Krobo	1081	Nsawam	Hospital	Nsawam	4930
Nsawam	Health Center	Nsawam	901	Adoagyiri	Health Center	Nsawam	817
Djankrom	Health Center	Nsawam	295	Klo Agogo	Polyclinic	Yilo Krobo	237
Nkurakan	Health Center	Yilo Krobo	469	Somanya	Polyclinic	Yilo Krobo	616

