### 4.0 Data Analysis (Aims 1-3)

Data on all patients randomly assigned to the intervention or control groups will be analyzed on an intention-to-treat basis. Deviations from randomized allocation will be reported. Summary statistics based on mean, standard deviation or frequency will be used to characterize the sample distribution of each arm. Proper transformations will be investigated and taken if the sample distributions of continuous variables violate the normality assumption. For Aims 1-3, generalized linear mixed models (GLMMs) will be used to test the differences between the two arms since cluster randomized control design is used. There are four components in GLMMs: outcome variable, fixed effects, random effect, and link function. The fixed effects include explanatory variable and covariates. In this study, all three aims have the same explanatory variable which is a binary variable indicating the arm to which women are assigned. The study sites, gestational age, and women's demographic variables such as education or literacy, marital status, pregnancy history, and medical history will be added to the GLMMs as covariates to increase the precision of estimates. The random effect is the 14 facilities. In this study, a random intercept model will be used to account for the cluster effect. The outcome variables and link functions in GLMMs depends on aims and are described below. The construct of GLMMs is to test if the explanatory variable is significant at 0.05 level using likelihood ratio test.

For **Aim 1** to quantify differences in the recognition of pregnancy and newborn danger signs and knowledge of recommended action steps, the BPCR Index will be measured at enrollment and third trimester. We will add baseline data as covariates. The logit link function will be used for each binary BPCR question to test the efficacy of the group-based ANC method. The identity link function will be used when the outcome variable is a summary statistic of the BPCR Index. When the p-value of the explanatory variable is less than 0.05, we will declare a significant difference between the two arms. Average changes in BPCR summary statistics or odds ratio in each question will be used to quantify the effect of the group-based ANC intervention.

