For **Aim 2** of assessing behavioral differences in care-seeking patterns between the two arms, the outcome variables are number of attendances in ANC visits, facility birth, and postnatal/partum care. For the attendance outcome variable, identity function will be used. For facility birth or postnatal/partum care, the logit link function is used. When the p-value of the explanatory variable is less than 0.05, we will declare a significant difference between the two arms. The effect of group-based ANC on attendances is quantified by the average difference. The effects of group-based ANC on facility birth and postnatal/partum care are quantified by odds ratio. For the secondary outcomes in aim 2, the logit or identity links will be used in the way similar to the primary outcomes.

For **Aim 3** to evaluate the clinical outcomes of mothers and their newborns, the outcome variables are maternal pregnancy-related morbidities and newborn birth status. For maternal morbidities, the logit link function is used. Since the newborn birth status is classified into three categories (stillbirth, live birth, and early neonatal mortality), cumulative logit link function is used. When the explanatory variable is significant at 0.05, the effect of group-based ANC on maternal pregnancy-related morbidities and newborn birth status are interpreted using odds ratio. We will illustrate the difference between outcomes using odds ratios for each pair of newborn birth status. The secondary outcomes are analyzed similarly using identity or logit link functions.

For the multiple outcomes in the same family, we will conduct direct inference using the Holm's multiple testing procedure to control familywise error rate at 0.05 level. The GLMM analysis will be carried out using lme4 package from R software. All findings will be reported using the Consolidated Standards of Reporting Trials (CONSORT) statement as a guide. Full transparency will be provided when reporting experimental details so that others may reproduce and extend our findings. We will register the study with clinicaltrials.gov and disclose all demographic and baseline characteristics, as well as primary and secondary outcomes.

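### Birth weight and admission haemoglobin are defined only by a cut-off, and no analysis of the measured values is named although they are recorded

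*Combined protocol and SAP*

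**What the plan says.** Section 2.0 lists six secondary outcomes for Aim 3. Two rest on a measured quantity, and each is defined by one cut: "Hemoglobin level upon hospital admission (dichotomized as normal or anemic (<9.5 g/dL))" and "Infant birth weight (normal vs. low (<2500g))". The other four are yes/no by nature: tetanus vaccination, neonatal tetanus protection, repeat pregnancy and exclusive breastfeeding.

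Section 3.3 says that midwives write "hemoglobin levels, newborn birth weight, maternal & newborn morbidities" and other items on the antenatal card, and that the research assistant collects them at every study visit except baseline.

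Section 4.0 says of Aim 3: "The secondary outcomes are analyzed similarly using identity or logit link functions". It does not match links to outcomes. It also says, for the analysis in general: "Proper transformations will be investigated and taken if the sample distributions of continuous variables violate the normality assumption". Neither sentence names birth weight in grams or haemoglobin in g/dL as something to be analysed.

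**The concern.** A single cut treats a 1500 g and a 2490 g infant as the same result, and a 2490 g and a 2510 g infant as opposite results. A haemoglobin rise from 9.6 to 11.5 g/dL would not register at all. If group care shifts the whole distribution, a comparison of proportions detects this less well than a comparison of means, and readers get no mean difference from which to judge its size.

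Precision is limited here because only 14 facilities are randomised. Birth weight also has a stated rationale: section 1.2 cites better birth weight outcomes with group care in other countries.

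The unassigned link is a second, smaller problem. An analyst could choose between mean and proportion after seeing the data and still be within the wording of section 4.0.

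**Working it through.** **Inputs from the documents.** "There are 14 sites in the study" (section 3.7), seven per arm. Section 3.0 gives the total: "1680 participants will be randomized into 120 groups of 12 to 14 women". The only derivation available for it is 120 × 14 = 1680. No power, effect size, SD, event rate or ICC accompanies it, so there is no power figure to reproduce. Mean facility size is m = 1680/14 = 120.

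**Assumptions not in the documents.** Roughly normal variable; the same shift for everyone; 10–30% below the cut; ICC (ρ) of 0.01, 0.02 or 0.05; equal facilities; no dropout; pair matching ignored.

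**Step 1: information kept without clustering.** With a proportion p below the cut, r = φ(z_p)² / [p(1 − p)]. For p = 0.10, z = −1.2816 and φ = 0.1755, so r = 0.1755²/0.09 = 0.342. For p = 0.15, 0.20 and 0.30, r = 0.426, 0.490 and 0.576. These figures ignore the facilities and so overstate the loss in this trial.

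**Step 2: with facilities.** Two approximations were used.
- A: the binary ICC is taken as r × ρ, giving r(1 + 119ρ) / (1 + 119rρ).
- B: [ρ + (1 − ρ)/m] / [ρ + (1 − ρ)/(m r)].

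Example of A at p = 0.10. For ρ = 0.01: 0.3422 × 2.19 / 1.4072 = 0.533. For ρ = 0.05: 0.3422 × 6.95 / 3.0361 = 0.783.

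Information kept by the binary version (A / B):

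| Below cut | ICC 0.01 | ICC 0.02 | ICC 0.05 |
|---|---|---|---|
| 10% | 0.53 / 0.54 | 0.64 / 0.64 | 0.78 / 0.79 |
| 15% | 0.62 / 0.62 | 0.72 / 0.72 | 0.84 / 0.84 |
| 20% | 0.68 / 0.68 | 0.76 / 0.77 | 0.87 / 0.88 |
| 30% | 0.75 / 0.75 | 0.82 / 0.82 | 0.90 / 0.91 |

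The loss shrinks as the ICC rises because variation between facilities limits both versions.

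**Step 3: power for an assumed shift of 0.2 SD.** Noncentral t on 12 df, two-sided 0.05, SE = √(2v/7). For the measured value v = ρ + (1 − ρ)/m. For the binary version v = ρ + (1 − ρ)/(m r), with r taken midway between the arms. At ρ = 0.01 the measured value has v = 0.01825, SE = 0.0722, and 0.2/0.0722 = 2.77, which gives power 0.720. The binary version at p = 0.10 has r = 0.308, v = 0.0368, SE = 0.1025, and 0.2/0.1025 = 1.95, which gives 0.435.

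| ICC | Measured | Binary, 10% | Binary, 30% |
|---|---|---|---|
| 0.01 | 0.720 | 0.435 | 0.586 |
| 0.02 | 0.536 | 0.358 | 0.454 |
| 0.05 | 0.299 | 0.240 | 0.274 |

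A simulation of 20,000 trials per scenario agrees closely for this shift: 0.72 against 0.43 (10%, ICC 0.01), 0.54 against 0.39 (15%, ICC 0.02) and 0.54 against 0.45 (30%, ICC 0.02).

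**The case against.** The strongest reply is that section 4.0 already covers this. It permits an identity link for Aim 3 secondary outcomes, and as all six are binary as listed, that link has a natural use only for birth weight or haemoglobin. It also provides for transforming continuous variables. This stands in part: a reader might infer that the plan rules out an analysis of means, and the documents do not support that. But the sentence may be generic, it assigns no link, and no outcome in grams or g/dL is defined for it to apply to.

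Second, the size of the loss rests on two quantities that the documents do not give. That stands. A reader might infer that most of the information is always lost. At an ICC of 0.05, or with a commoner abnormality, the loss is modest.

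Third, a reader might infer that these are among the few Aim 3 clinical outcomes that are not rare. The documents give no event rate for any of them, so this cannot be checked.

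Fourth, the cut-offs are pre-specified and clinically readable, and a benefit confined to the lower tail would show mainly in the proportion. Section 1.2 does not say whether the better birth weight outcomes elsewhere were means or rates. This is a good reason to keep the binary outcomes, but not to leave the means out.

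Finally, availability of the values is inferred from section 3.3. The indicator list that it mentions is not shown, and completeness of admission haemoglobin is not stated.

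**Conclusion.** The point holds as a minor one. Both outcomes are defined only as binary, their measured values appear to be collected, and no analysis of means is named. Under the assumptions listed, the binary version keeps about 53–75% of the information at an ICC of 0.01, 64–82% at 0.02 and 78–91% at 0.05, each range running over 10–30% below the cut and both approximations. The same table serves for haemoglobin, whose prevalence below 9.5 g/dL is equally unstated. The direction is the same in every scenario examined, but the size could be anything from substantial to modest. The figures apply to a uniform shift, not to a change confined to low values. These are secondary outcomes, so no primary conclusion of the trial depends on this.

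**What to change.** In sections 2.0 and 4.0:

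- Keep the two binary outcomes, analysed with the logit link and reported as odds ratios.
- Add birth weight in grams and haemoglobin in g/dL as named analyses, using the identity-link mixed model with a random facility intercept that section 4.0 already plans. Report mean differences with confidence intervals.
- State which link applies to each Aim 3 secondary outcome.
- State in advance which version of each of the two outcomes enters the Holm family.

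The cost is two further analyses and a change to the outcome list as well as to the analysis text. Section 4.0 promises registration and disclosure of the secondary outcomes, so the registered list should match. On the documents as they stand, no new data and no new type of model are needed, provided the card values are abstracted as numbers; the data collection form should be checked for this.
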